4.5 Stopping Criteria

Reasons for terminating the study may include but are not necessarily limited to the following:

- The incidence or severity of AEs indicates a potential health hazard to subjects.
- Advice of DSMB
- Subject enrollment is unsatisfactory.

If the study is discontinued, all assessments listed in the end of treatment visit should be completed.

4.6 Data Collection for Withdrawn Subjects

Data of withdrawn subjects will be collected up to the point of withdrawal. This data will still be included in the pooled data of the study for further analysis. For subjects who withdraw from further data collection, there will not be replacement with more subjects. When study drug is discontinued (regardless of the reason), the investigator will encourage that all of the evaluations required at the End of Treatment Visit be performed and that any additional evaluations be completed that may be necessary to ensure that the patient is free of untoward effects. The patient will be encouraged to seek appropriate follow-up for any continuing health problems.

5 Study Drug

5.1 Entresto (sacubitril/valsartan)

Sacubitril is a molecule that inactivates neprilysin, a neutral endopeptidase responsible for degrading natriuretic peptides. Sacubitril cannot be given alone as it raises the levels of angiotensin II 62-64 and for this reason is combined with valsartan, an angiotensin II receptor blocker 65. This combination, sacubitril/valsartan [LCZ696 (Entresto), Novartis Pharmaceuticals Corp.], has been given to patients with heart failure raising serum and urinary levels of cGMP, a marker of NPs activity, by 35% and 25%, respectively 24 and decreases mortality in this type of patients 25. Entresto is currently approved by the FDA for the treatment of patients with heart failure NYHA Class II-IV 26.

5.1.1 Description

ENTRESTO contains a complex comprised of anionic forms of sacubitril and valsartan, sodium cations, and water molecules in the molar ratio of 1:1:3:2.5, respectively. Following oral administration, the complex dissociates into sacubitril (which is further metabolized to LBQ657) and valsartan. The complex is chemically described as Octadecasodiumhexakis(4-[[[(1S,3R)-1-([1,1'-biphenyl]-4-ylmethyl)-4-ethoxy-3-methyl-4-oxobutyl]amino]-4-oxobutanoate)hexakis(N-pentanoyl-N-{[2'-(1H-tetrazol-1-ylid-5-yl)[1,1'-biphenyl]-4-yl]methyl}-L-valinate)—water (1/15). Its empirical formula (hemipentahydrate) is C₄₈H₅₅N₆O₈Na₃ 2.5 H₂O. Its molecular mass is 957.99 M.

5.2 Dosage and Administration

Entresto will be given orally at the recommended starting dose of 49/51 mg twice-daily. The dose of Entresto should be doubled after 2 to 4 weeks to the target maintenance dose of 97/103 mg twice daily, as tolerated by the patient ^{25,60}.

12 Weeks of Treatment

We will follow the recommended dosages as reported in the Entresto prescribing information sheet distributed by: Novartis Pharmaceuticals Corporation East Hanover, New Jersey 07936. Subjects will initiate with the recommended dose of 49/51 mg (sacubitril/valsartan) twice daily for two weeks. For

Table 1. Criteria to lower dosage or discontinuation of Entresto
1. Hypotension (symptomatic hypotension or orthostatic hypotension, or hypotension that requires treatment)
2. Renal failure. Increase in creatinine > 50% of baseline value.
3. Hyperkalemia. K ⁺ > 5.2 mEq/L
4. Falls (related to hypotensive episodes)
5. Angioedema
Hypotension = a decrease from baseline in sitting systolic blood pressure (SBP) of ≥ 20 mm Hg and a decrease in sitting SBP to < 90 mm Hg or symptoms.

patients not currently taking an angiotensin-converting enzyme inhibitor (ACEi) or an angiotensin II receptor blocker (ARB) or previously taking a low dose of these agents we will initiate treatment with the lowest dose available (24/26) (sacubitril/valsartan) twice daily. After two weeks of treatment the study physician will progressively increase to the target maintenance dose of 97/103 mg (sacubitril/valsartan). Each participant will receive a package with enough pills containing Entresto/placebo that will last until the following schedule visit. To assure adherence to the treatment,

patients will return all the packages with the empty vials at each study visit. Participating patients will be encouraged to follow their standard health care treatment and lifestyle recommendations prescribed

by their attending physician.

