7. History of angioedema related to use of angiotensin convertase enzyme inhibitor (ACEInh) or angiotensin receptor blocker (ARB).
8. Current use of ACEInh or ARB
9. Concomitant use with aliskiren (renin inhibitors) in patients with diabetes.
10. Renal artery stenosis of more than 60% occlusion in any of the renal arteries by duplex ultrasound.
11. Patients on therapy with lithium compounds.
12. Women who are pregnant or nursing. Women who are not postmenopausal (≥ 12 months of non-therapy- induced amenorrhea) or surgically sterile are defined as being of child-bearing potential, must have a negative result from a urine pregnancy test at Visits 1 and 2. Women with the potential to become pregnant who are not willing to use an acceptable form of birth control, defined as abstinence or use of an intrauterine device (IUD), oral contraceptive, barrier and spermicide, or hormonal implant throughout the study period.
13. Patients with implantable cardiac defibrillators
14. Patients with hyperkalemia (K⁺ > 5.2 mEq/L) and patients with conditions that are the most frequent cause of hyperkalemia, such as CKD and ESRD
15. Patients on potassium sparing diuretics

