5.2.1 Dose Adjustment

Dose of Entresto is started at the middle level of 49/51 mg twice-daily and if well tolerated by the patient then dosage is increased to the target maintenance dose described above. If manifestations of side effects of Entresto appear (Table 1), dose can be lowered to the lowest dose of 24/26 mg twice-daily. If at the lowest dose level adverse events continue then patient will be withdrawn from the study. Dose of Entresto will be administered following the recommendation as written in the Entresto prescribing information sheet from Novartis Pharmaceuticals Corporation East Hanover, New Jersey 07936 as revised by the FDA on August, 2015 (Patient information sheet attached). The study physician [name] will be responsible for all dose changes in subjects participating in this study. Specific guidelines on dosage change are detailed below.

Dosage modifications guidelines:

Any patient with a serum potassium > 5.2 mEq/L after randomization requires regular, repeated checks of potassium concentration (beyond that prescribed in the protocol) until it is clear that the potassium concentration is stable and not rising into the range of concern (≥ 5.5 and < 6.0 mEq/L) or potential danger (≥ 6.0 mEq/L).

Corrective action for management of hyperkalemia.

Serum potassium > 5.2 and less than or equal to 5.5 mEq/L

- Confirm potassium concentration in a non-hemolyzed sample.
- Reinforce low potassium diet and restriction of food/drinks with high potassium content (e.g. orange juice, melon, bananas, low-salt substitutes etc.).
- Review medical regimen (including dietary supplements and over-the-counter medications) for agents known to cause hyperkalemia. Consider reduction in dose or discontinuation of these agents:
 - Potassium supplements, e.g., potassium chloride.
 - Salt substitutes.
 - Non-steroidal anti-inflammatory drugs (NSAIDs)
 - Herbal Supplements:
 - For example, Noni juice, alfalfa (*Medicago sativa*), dandelion (*Taraxacum officinale*), horsetail (*Equisetum arvense*), nettle (*Urtica dioica*), milkweed, lily of the valley, Siberian ginseng, hawthorn berries.
- Repeat serum potassium measurement within 3 to 5 days.
- If serum potassium remains > 5.2 and ≤ 5.5 mEq/L, regularly monitor serum potassium levels to ensure stability (suggested once monthly).
- Consider down-titration of study medication, according to study physician medical judgment.

Serum potassium > 5.5 and < 6.0 mEq/L

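### Sections 5.2 and 5.2.1 give two starting doses about twofold apart (24/26 mg and 49/51 mg), and the single increase in section 6.2 fits only the higher one

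*Combined protocol and SAP*

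**What the plan says.** **Section 5.2 (Dosage and Administration)** states the general rule: "Subjects will initiate with the recommended dose of 49/51 mg (sacubitril/valsartan) twice daily for two weeks". It then makes an exception for "patients not currently taking an angiotensin-converting enzyme inhibitor (ACEi) or an angiotensin II receptor blocker (ARB) or previously taking a low dose of these agents", for whom "we will initiate treatment with the lowest dose available (24/26) (sacubitril/valsartan) twice daily". On the step up, its opening paragraph says "The dose of Entresto should be doubled after 2 to 4 weeks to the target maintenance dose of 97/103 mg twice daily", as tolerated. Later it has the study physician raise the dose progressively to target after two weeks.

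**Section 4.2 (Eligibility Criteria)**, exclusion 8, rules out "Current use of ACEInh or ARB".

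**Section 5.2.1 (Dose Adjustment)** says "Dose of Entresto is started at the middle level of 49/51 mg twice-daily", followed by an increase to target if tolerated. The lowest strength appears only as a response to side effects: "dose can be lowered to the lowest dose of 24/26 mg twice-daily".

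**Section 5.5 (Blinding of Study Drug)** has the investigational pharmacy randomise the participant, prepare the first two weeks of treatment and make capsules at all three strengths. The blinded study physician provides the capsules under the procedures in 5.2.1.

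**Section 6.2 (Treatment Period)** lists a move to the target dose at week 2. At weeks 4 and 6 it lists only reductions.

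Sections 5.2, 5.2.1 and 10 all refer to the manufacturer's prescribing information sheet. It is described as attached to the protocol but is not in the documents available for this review.

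**The concern.** One eligible patient has two written starting doses. A reader of 5.2 would start a patient who takes no ACE inhibitor or ARB at 24/26 mg. A reader who goes from 5.5 to 5.2.1 would start the same patient at 49/51 mg.

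The disagreement falls in the first weeks on a drug that lowers blood pressure, when tolerance is first tested. The protocol treats this as a real risk: Table 1 in section 5.2 lists hypotension and related falls as reasons to lower or stop the dose, and Table 2 in section 11.1 reports hypotension in 18% of Entresto patients in the cited heart-failure trial. If staff resolve the conflict case by case, early adverse events in the active group would come from a mixture of starting doses that the protocol does not define.

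**Working it through.** **1. Who falls under the 24/26 mg rule.** Two readings of the exception in 5.2 are possible.

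- *Plain wording.* The rule covers patients not currently on an ACE inhibitor or ARB. Exclusion 8 removes all current users, so everyone eligible is covered and the general 49/51 mg rule applies to nobody.
- *Narrower reading.* The rule covers patients with no prior use or only low-dose prior use, and 49/51 mg is left for former users of higher doses. In favour of this reading, the clause on previous low-dose use would be redundant if every non-user were already covered.

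Section 5.2.1 conflicts with both readings, because it states a 49/51 mg start without separating any group.

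**2. Size of the gap at the first dose.** Strengths are from 5.2 and 5.5.

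- Sacubitril: 49 / 24 = 2.04
- Valsartan: 51 / 26 = 1.96

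**3. Which start fits section 6.2.**

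- From 49/51 mg, target is one doubling away (97 / 49 = 1.98; 103 / 51 = 2.02).
- From 24/26 mg, it is two doublings away, through 49/51 mg.
- Section 6.2 lists one increase, so it matches a 49/51 mg start only.

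**4. Exposure under each schedule.** Twice-daily dosing is 14 doses a week. Assumptions: full adherence, no dose reduction and two-week steps. The two-week step from 24/26 mg is an assumption, since 5.2 gives no date for the intermediate dose.

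- *Schedule A:* 49/51 mg for 2 weeks, then 97/103 mg for 10 weeks.
- *Schedule B:* 24/26 mg for 2 weeks, 49/51 mg for 2 weeks, then 97/103 mg for 8 weeks.

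| | Schedule A | Schedule B | B relative to A |
|---|---|---|---|
| Sacubitril, weeks 1–2 | 49×28 = 1,372 mg | 24×28 = 672 mg | about half |
| Sacubitril, weeks 1–4 | (49+97)×28 = 4,088 mg | (24+49)×28 = 2,044 mg | half |
| Sacubitril, 12 weeks | 49×28 + 97×140 = 14,952 mg | 24×28 + 49×28 + 97×112 = 12,908 mg | 13.7% less |
| Valsartan, 12 weeks | 51×28 + 103×140 = 15,848 mg | 26×28 + 51×28 + 103×112 = 13,692 mg | 13.6% less |

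If the 49/51 mg step lasts four weeks in both schedules, as 5.2 allows, 12-week sacubitril is 49×56 + 97×112 = 13,608 mg against 24×28 + 49×56 + 97×84 = 11,564 mg, which is 15.0% less. These figures price the choice of schedule. They do not measure harm.

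**5. Safety checks after reaching target.** Under schedule B, target is reached at week 4. The next scheduled potassium, creatinine and clinic blood pressure checks come at week 6 in section 6.2, section 11.2 and footnote 3 of the Schedule of Events, but at week 8 in the schedule table itself. That is two weeks at full dose in one case and four in the other, so this discrepancy has to be settled with the starting dose.

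**The case against.** The best defence is that 5.2.1 sits under 5.2 and refers back to it. On that view 5.2 gives a general rule and a specific exception, the exception governs, and 5.2.1 merely restates the general case. Both sections also adopt the prescribing sheet, and section 10 has the study physician adjust doses from that sheet, so staff with the sheet in hand may well reach one sensible answer. Both starts are below target, the difference lasts roughly two to four weeks, and home blood pressure readings, a week 1 call and week 2 laboratory tests are in place.

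Much of this stands: it makes a sensible resolution on site plausible and limits the consequence. It does not remove the conflict. Nothing ranks 5.2 above 5.2.1, section 5.5 points to 5.2.1 alone, and 6.2 fits only the higher start. The physician's responsibility for dose changes does not say which starting dose is meant.

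A reader might infer two stronger points that the documents do not support.

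- *The pharmacy follows one section and the physician another.* Nothing directs the pharmacy to 5.2. It prepares all three strengths, the physician provides them, and each patient receives one first dose.
- *Patients starting at 24/26 mg would jump about fourfold to target at week 2.* Section 5.2 calls for a progressive increase, and the only strength between the two is 49/51 mg.

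**Conclusion.** The concern holds as a conflict between stated dosing rules. On plain wording it reaches every eligible patient, and on the narrower reading those with no or only low-dose prior use of an ACE inhibitor or ARB. The first doses differ about twofold, and sacubitril over the first four weeks differs by half under two-week steps and full adherence.

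The consequence is a short early-tolerability and safety issue. It should be fixed, because the rules bear on patient safety and the remedy is cheap. Two further conclusions might be drawn and should not be. The documents do not show that either starting dose is wrong, since the prescribing sheet is not available here. Nor do they show damage to the sample size or the week 12 comparison: the sample size calculation does not use the starting dose, and under the two-week schedules above target is reached by week 4 at the latest if tolerated.

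**What to change.** Make 5.2, 5.2.1 and 6.2 state one schedule, and confirm the capsule steps with the investigational pharmacy.

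- **If the 24/26 mg rule stands:** start at 24/26 mg, step to 49/51 mg at week 2 and to 97/103 mg at week 4 as tolerated. Change 6.2 to allow the week 4 increase and bring 5.2.1 into line. In the same amendment, set the third on-treatment visit at week 6 throughout, so that potassium, creatinine and blood pressure are checked two weeks after target is reached. If former users of higher doses are meant to start at 49/51 mg, say so and define a low dose.
- **If 49/51 mg is intended for all:** delete the 24/26 mg starting rule from 5.2.

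The cost is amendment wording. No visit is added, because drug is already dispensed at week 4. The first option reaches target about two weeks later, with about 14% less cumulative sacubitril over 12 weeks under full adherence. Fixing the third visit at week 6 also leaves six weeks until the week 12 laboratory tests, against four if it were at week 8. The second option has no delay but gives up the gentler start that 5.2 now provides.

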5.2.1 Dose Adjustment

Dose of Entresto is started at the middle level of 49/51 mg twice-daily and if well tolerated by the patient then dosage is increased to the target maintenance dose described above. If manifestations of side effects of Entresto appear (Table 1), dose can be lowered to the lowest dose of 24/26 mg twice-daily. If at the lowest dose level adverse events continue then patient will be withdrawn from the study. Dose of Entresto will be administered following the recommendation as written in the Entresto prescribing information sheet from Novartis Pharmaceuticals Corporation East Hanover, New Jersey 07936 as revised by the FDA on August, 2015 (Patient information sheet attached). The study physician [name] will be responsible for all dose changes in subjects participating in this study. Specific guidelines on dosage change are detailed below.

Dosage modifications guidelines:

Any patient with a serum potassium > 5.2 mEq/L after randomization requires regular, repeated checks of potassium concentration (beyond that prescribed in the protocol) until it is clear that the potassium concentration is stable and not rising into the range of concern (≥ 5.5 and < 6.0 mEq/L) or potential danger (≥ 6.0 mEq/L).

Corrective action for management of hyperkalemia.

Serum potassium > 5.2 and less than or equal to 5.5 mEq/L

- Confirm potassium concentration in a non-hemolyzed sample.
- Reinforce low potassium diet and restriction of food/drinks with high potassium content (e.g. orange juice, melon, bananas, low-salt substitutes etc.).
- Review medical regimen (including dietary supplements and over-the-counter medications) for agents known to cause hyperkalemia. Consider reduction in dose or discontinuation of these agents:
 - Potassium supplements, e.g., potassium chloride.
 - Salt substitutes.
 - Non-steroidal anti-inflammatory drugs (NSAIDs)
 - Herbal Supplements:
 - For example, Noni juice, alfalfa (*Medicago sativa*), dandelion (*Taraxacum officinale*), horsetail (*Equisetum arvense*), nettle (*Urtica dioica*), milkweed, lily of the valley, Siberian ginseng, hawthorn berries.
- Repeat serum potassium measurement within 3 to 5 days.
- If serum potassium remains > 5.2 and ≤ 5.5 mEq/L, regularly monitor serum potassium levels to ensure stability (suggested once monthly).
- Consider down-titration of study medication, according to study physician medical judgment.

Serum potassium > 5.5 and < 6.0 mEq/L

- Confirm potassium concentration in a non-hemolyzed sample.
- Consider down-titration or temporarily discontinue study drug according to study physician medical judgment.

- Apply all measures outlined for serum potassium > 5.2 and ≤ 5.5 mEq/L.
- Repeat serum potassium measurement after 2-3 days.
- If serum potassium < 5.5 mEq/L, consider resumption of study drug at lower dose with repeat potassium within 5 days.

Serum potassium greater than or equal to 6.0 mEq/L

- Immediately discontinue study drug.
- Confirm potassium concentration in a non-hemolyzed sample.
- Urgently evaluate patient and treat hyperkalemia as clinically indicated.
- Apply all measures outlined for serum potassium > 5.2 and < 6.0 mEq/L.
- No resumption of study drug without individualized case discussion with and permission from the DSMB.

Guidelines for the management of renal dysfunction

If, at any time after randomization, eGFR decreases by $\geq 25\%$ from baseline (or if serum creatinine concentration increase to 2.5 mg/dL or by 50% of baseline value, the investigator will check for potentially reversible cases of renal dysfunction such as:

- Non-steroidal anti-inflammatory drug intake, antibiotics, or other treatments known to affect creatininemia
- Volume decrease
- Urinary infection
- Urinary tract obstruction
- Study medication

If a patient eGFR decreases by $\geq 40\%$ from baseline (or if serum creatinine concentration rises above 3 mg/dL, the investigator will check for potentially reversible causes of renal dysfunction (see above). If the study physician judges that the study medications needs to be stopped, the principal investigator needs to be informed and the DSMB contacted.

Guidelines for the management of blood pressure

If symptomatic hypotension occurs:

- Correct any treatable cause, e.g. hypovolemia.
- If hypotension persists, the study drug should be down-titrated or withdrawn at the judgment of the study physician.

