5.5 Blinding of Study Drug

Blinding of the drug will be done by the investigational Drug Services (IDS) at the University of Minnesota. Once a subject is eligible to participate in the study, the PI will inform IDS and they will

be in responsible for randomizing the subject into one of the two groups and preparing the first two weeks of treatment. Capsules containing pills with either placebo or Entresto will be placed in a container identified with a code, which will be kept by IDS pharmacy unless it is requested as part of an emergency response or study termination. Each individual pill will be packaged in identical capsules by IDS pharmacy staff. Entresto comes in pills of three dosages: 24/26 mg, 49/51mg and 97/103 mg. Capsules for each of the three dosages (placebo or Entresto) will be prepared by IDS and the study physician (blinded) will provide the capsules following the dosing procedures as described in 5.2.1. The subject will only be unblinded if there is a medical situation where it is necessary to know if the subject is on drug or placebo.

[figure not shown]

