11.1 Potential Risks

As part of the PARADIGM-HF clinical trial adverse reactions occurring at an incidence of $\geq 5\%$ in patients who were treated with ENTRESTO in the double-blind period are shown in Table 2.

Table 2. Adverse effects and percentage of cases in the PARADIGM-HF.

Adverse effects	Entresto	Placebo + Enalapril	Preventive or corrective action
Angioedema, %	0.5	0.2	Discontinue
Hypotension, %	18	12	Dose adjustment of blood pressure lowering medications
Serious hypotension, %	1.5	1.5	Dose adjustment of blood pressure lowering medications
Renal failure, %	5	5	Monitor creat and blood urea
Hyperkalemia	12	14	Monitor K+
Cough, %	9	13	Modify dose
Dizziness, %	6	9	Prevent hypotension
Falls, %	1.90	1.30	Prevent hypotension

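### Section 5.2.1 permits dose lowering after angioedema, while the protocol's own risk table (Table 2) gives discontinuation as the action

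*Combined protocol and SAP*

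**What the plan says.** The instructions on angioedema are spread over several sections of the combined protocol and SAP.

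- **Section 5.2, Table 1.** The heading is "Table 1. Criteria to lower dosage or discontinuation of Entresto". Angioedema is item 5, after hypotension, renal failure, hyperkalemia and falls. No item is tied to one action or the other.
- **Section 5.2.1, general rule.** "If manifestations of side effects of Entresto appear (Table 1), dose can be lowered to the lowest dose of 24/26 mg twice-daily". The next sentence reads: "If at the lowest dose level adverse events continue then patient will be withdrawn from the study".
- **Section 5.2.1, specific guidelines.** The section announces: "Specific guidelines on dosage change are detailed below". What follows covers potassium, renal function and blood pressure only.
- **Section 5.5.** The blinded study physician "will provide the capsules following the dosing procedures as described in 5.2.1", so 5.2.1 is the rule in use when capsules are handed out.
- **Section 11.1, Table 2.** The row reads "Angioedema, % 0.5 0.2 Discontinue". The last column is for preventive or corrective action.
- **Section 11.3.** For a serious adverse event in general, the drug is either stopped or its dose adjusted, as the study physician judges. Angioedema is not named.

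**The concern.** The operative dosing rule and the risk table do not say the same thing about one named event. Read alone, 5.2.1 lets the study physician move a patient with angioedema down to 24/26 mg twice daily and continue, with withdrawal compulsory only if the event persists there. Read alone, Table 2 says to stop. Whether the drug is stopped at once should not depend on which section the physician has open.

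What is at stake is the safety of the occasional patient who develops angioedema on treatment. Sample size, power, type I error and the efficacy analysis are not involved.

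**Working it through.** **Comparison of the texts**

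1. *Does Table 1 settle the action?* No. Its heading pools the triggers for lowering with those for stopping and assigns neither to angioedema.
2. *Does the general rule in 5.2.1 except angioedema?* No. It refers to Table 1 as a whole and offers dose lowering.
3. *Do the specific guidelines in 5.2.1 supply a stop?* Not for angioedema. They do for potassium: at 6.0 mEq/L or above the drug is stopped immediately and may not be resumed without DSMB permission. The protocol can therefore write a mandatory stop into this section, and has not done so here.
4. *Does Table 2 distinguish stopping from adjusting?* Yes. Cough calls for a dose change, hypotension for adjusting blood-pressure-lowering drugs, and renal failure and hyperkalemia for monitoring. Angioedema is the only row with discontinuation.
5. *Does 11.3 close the gap?* No. Its general sentence also leaves dose adjustment open.

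So 5.2.1 permits an action that Table 2 does not offer for this event, and no section withdraws the permission.

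**When a lower dose exists**

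Exclusion 8 removes current users of an ACE inhibitor or ARB. Those who remain are not taking these agents, and 5.2 starts such patients at 24/26 mg. On that rule nothing lower is available until the increase after two weeks, so lowering is possible in at most 12 − 2 = 10 of the 12 weeks. On the 49/51 mg start stated in 5.2.1 it is possible in all 12.

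**Scale**

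The plan gives no figure of its own to reproduce. Inputs: p = 0.005 (Table 2, Entresto column, from a heart-failure trial) and n = 15 active patients (section 9.2).

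- Expected cases: n × p = 15 × 0.005 = 0.075.
- Chance of at least one case: 1 − (1 − p)^n = 1 − 0.995^15 = 0.072, about 7%.
- Half the rate (assumed): 1 − 0.9975^15 = 0.037.
- Double the rate (assumed): 1 − 0.99^15 = 0.140.

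The documents give neither the follow-up time behind the 0.5% nor a rate in PAD patients, so using it for 12 weeks of treatment is an assumption. The results are chances that the event occurs. Harm from continued dosing would also need the physician to choose lowering over stopping, and the documents give no rate for that.

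**The case against.** The strongest reply is that there is no contradiction. Table 1 covers discontinuation as well as lowering, 5.2.1 is permissive, and a physician who stops the drug complies with every section. On this view the general text offers two actions and the specific row in Table 2 picks one. This stands to a point: a reader might infer that 5.2.1 orders continued dosing after angioedema, and it does not. It remains true that stopping is nowhere required in the section the physician is told to follow.

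Table 2 can also be called a summary, since its potassium and renal entries are much shorter than the rules in 5.2.1. That is fair. But if Table 2 is only a summary, the protocol text has no operative angioedema stop at all, which leaves the case for adding one intact.

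Section 5.2.1 also ties dosing to the August 2015 prescribing information, which is not in the supplied documents. That sheet may settle the matter, but this cannot be checked here, and it would not remove the protocol's own sentence.

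Other safeguards are real. One study physician is responsible for all dose changes, the DSMB draws up safety guidelines before recruitment, and all adverse events are reported to it with its recommendations followed. Reporting to the DSMB comes after the event, however, and is not a stop written into the dosing rules.

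Two stronger readings should be resisted. Exclusion 7 bars "History of angioedema related to use of angiotensin convertase enzyme inhibitor (ACEInh) or angiotensin receptor blocker (ARB"), and the study drug contains an ARB (5.1: "for this reason is combined with valsartan, an angiotensin II receptor blocker"). A reader might infer that 5.2.1 therefore breaches the eligibility rules. It does not: exclusion 7 is an entry criterion about history and does not govern management on treatment. Nor do the documents support a permanent ban on restarting. Table 2 says to discontinue and is silent on resumption.

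**Conclusion.** The inconsistency holds in limited form. For angioedema, the operative dosing section permits dose lowering and does not require stopping, while Table 2 gives discontinuation. It should be corrected because it concerns patient safety and the remedy is a few words, not because it is likely to arise often.

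If the 0.5% heart-failure rate carried over to 15 active patients, the chance of seeing at least one case would be about 7%, or 4% to 14% at half to double that rate. These figures give scale only and do not measure harm. The conclusion itself rests on the wording and not on the rate. It is conditional on the prescribing information, which could not be consulted. No effect on power or on the efficacy result follows.

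**What to change.** Three edits:

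1. In Table 1, label item 5: *Angioedema: discontinue*.
2. In the specific guidelines of 5.2.1, add: *Angioedema: immediately discontinue study drug; dose lowering does not apply.*
3. In 11.3, make the sentence on serious adverse events subject to the mandatory stops in 5.2.1.

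If the sponsor wants a rule on resumption, the most that the protocol's own practice supports is to mirror the potassium rule at 6.0 mEq/L or above: no resumption without DSMB permission. That would be a proposal and not something the documents already require.

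The cost is one label, one line and one clause. Visits, sample size and analysis do not change.
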